#### 8.2.1 Sample size justification

No formal sample size calculation has been performed for this study. The sample size required for the trial is at least 40 randomized paediatrics subjects recruited from sites within the European Union and Canada. This sample size is considered adequate to achieve the study objectives and provide sufficient information to evaluate data descriptively.

Page 6 of 18 Version: AMENDMENT 1 Date: July 1, 2019

### 8.3 Secondary effectiveness analysis

The following secondary effectiveness endpoints will be summarized descriptively by treatment group for the FAS:

- Haemostasis at 4 minutes following randomization;
- Haemostasis at 7 minutes following randomization;
- Haemostasis at 10 minutes following randomization;
- Incidence of treatment failures (defined as haemostasis not achieved within 10 minutes or bleeding at the TBS during the ten-minute observational period that requires further hemostatic measures, other than re-application of the assigned hemostatic adjunct).

Two-sided 95% CIs for the proportions of subjects with hemostasis at 4 minutes, 7 minutes, and 10 minutes, will be constructed for each treatment group separately ( $P_E$  for EVICEL and  $P_C$  for Control), using the Clopper-Pearson method. In addition, for each time point, a two-sided 95% CI will be reported for the ratio proportion of successes (hemostasis achieved) in the EVICEL group/proportion of successes in Control group ( $P_E/P_C$ ), using the Farrington-Manning score method.

## 8.4 Analysis of follow-up data

The following follow-up data will be summarized descriptively for post-surgery to hospital discharge (within 72 hours prior to discharge) and for 30-day (±14 days) visit:

- Re-hospitalizations and surgical procedures since hospital discharge [for 30-day (±14 days) visit only];
- Relevant changes in medical history since screening;
- Presence of clinically significant changes to subject since baseline;
- Presence and duration of subject presence in elevated care unit (ICU, step-down unit, etc.);
- Presence and duration of subject being on ventilator post-operatively;
- Laboratory data (full blood count with white blood cell differential, and coagulation parameters) (only for post-surgery to hospital discharge within 72 hours prior to discharge).

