1. INTRODUCTION

Bleeding during surgical procedures may manifest in many forms. It can be discrete or diffuse from a large surface area. It can be from large or small vessels; arterial (high pressure) or venous (low pressure) of high or low volume. It may be easily accessible or it may originate from difficult to access sites. The bleeding tissues may be firm or friable.

Conventional methods to achieve haemostasis include use of surgical techniques, sutures, ligatures or clips, and energy-based coagulation or cauterisation. When these conventional measures are ineffective or impractical, adjunctive haemostasis techniques and products are typically utilised, including topical absorbable haemostats such as oxidised regenerated cellulose, gelatin, or collagen and active haemostats such as topical thrombin or fibrin sealants.

Fibrin sealants are typically dual component systems consisting of virus-inactivated, human plasma-derived thrombin and fibrinogen. The two components are mixed during application to a target site and upon combination mimic the final step in the coagulation pathway to form a stable, physiological fibrin clot that assists in healingⁱ. The fibrinogen component may also contain anti-fibrinolytic agents. Fibrin sealants have proven to be valuable adjuncts for haemostasis in a variety of surgical and endoscopic procedures. They have been successfully used as biodegradable topical agents for haemostasis, wound healing, or tissue sealing purposes in cardiovascular, thoracic, neurologic, gastrointestinal, urologic, gynaecologic, hepatic and plastic and reconstructive surgical procedures^{ii,iii,iv,v,vi}. They have also been evaluated in bleeding from soft tissue tumour beds or parenchymal organs following surgical resection^{vii}. Fibrin sealants have been shown to reduce post-operative complications, including blood loss and reduce the need for repeated procedures by promoting wound healing^{viii}.

EVICEL® is a topical haemostat and will be evaluated in this study to measure its safety and effectiveness in controlling mild/moderate bleeding from soft tissue as required by the Paediatric Investigational Plan.

The Product

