7.1.4 Post-Surgery until Hospital Discharge

Prior to discharge, the following blood samples must be drawn and data will be recorded:

- Post-operative blood samples will be taken for Full Blood Count (FBC) with Differential and Coagulation parameters (PT, aPTT, INR). The last set of blood samples taken prior to discharge will be recorded:
- Physical examination as per institutions normal procedure;
- Concomitant medications;
- Details of hospital stay including: date of hospital discharge; overall stay in days (admission to discharge); ventilator time (if applicable);
- Incidence of adverse events; and
- Incidence of potential bleeding-related complications, including thrombotic events.

7.1.5 30-day Follow-Up Visit (±14 days)

The following information will be recorded during and in person visit or phone call, approximately 30 days following surgery:

- Changes in concomitant medications, including use of any blood products following hospital discharge;
- Incidence of adverse events; and
- Incidence of potential bleeding-related complications, including thrombotic events.

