9.2.8 Collection of Adverse Events

AEs will be recorded as they are reported, whether spontaneously volunteered or in response to questioning about well-being. AEs will be collected from the point of randomization during the surgical procedure, throughout the hospital admission, and until completion of the 30-day follow-up visit.

All AEs will be documented in the subject's source documents (e.g. medical records) and eCRF. All AEs will be followed until completion of the 30-day follow-up visit or until a stable resolution, whichever is sooner.

Details of all AEs occurring during the study must be recorded on the AE form with the following information:

- Description of the event;
- Dates of onset and resolution;
- Severity;
- Action taken;
- Outcome;
- Relationship to investigational product; and
- Whether the AE is serious or not.

Expectedness of an SAE will be defined based on whether the specificity or severity of which is not consistent with the current investigator brochure.

Other: The investigator may also need to consider whether an event is attributable to the investigational product, based on insufficiencies or inadequacies in the instructions for use or as a result of user error. The investigator must contact the Sponsor should this occur.

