- 2. The investigator must perform the surgical procedure according to his/her standard of care.
- 3. Once the investigator encounters an appropriate soft tissue or parenchymal organ TBS related to the primary operative procedure, randomization should immediately take place.

Subjects will be followed post-operatively through discharge and at 30 days (±14 days) post-surgery.

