2.2.2	Haemostasis at 7 minutes following randomization – FAS	Discrete data Includes 95% CI for proportion of subjects with hemostasis at 7 minutes separately for each group, as well as 95% CI for the ratio of proportions	G2
2.2.3	Haemostasis at 10 minutes following randomization – FAS	Discrete data Includes 95% CI for proportion of subjects with hemostasis at 10 minutes separately for each group, as well as 95% CI for the ratio of proportions	G2

No	Title of table/figure	Notes	Shell 
2.2.4	Incidence of treatment failures (defined as haemostasis not achieved within 10 minutes or bleeding at the TBS during the ten-minute observational period that requires further hemostatic measures, other than reapplication of the assigned hemostatic adjunct) – FAS	Discrete data	G2
2.3	Follow-up assessments		G.S.
2.3	Post-surgery to hospital discharge (within 72 hours prior to discharge) and 30- day (±14 days) follow-up assessments – FAS	Indication of re-hospitalizations since hospital discharge (d), indication of surgical procedures since hospital discharge [both for 30-day (±14 days) visit only] (d), indication of relevant changes in medical history since screening (d), presence of clinically significant changes to subject since baseline (d), subject presence in elevated care unit (ICU, step-down unit, etc.) (d), duration of subject presence in elevated care unit (ICU, step-down unit, etc.) (c), subject presence on ventilator post-operatively (d), duration of subject being on ventilator post-operatively (c), length of subject hospital stay from admission to discharge (days) (c), and length of subject hospital stay from procedure to hospital discharge (days) (c)	G2
3	Safety data		
3.1	Adverse Events		
3.1.1	Number of subjects experiencing any during/post treatment AE by category – Safety analysis set		AS
3.1.2	Adverse events (during/post treatment) by subject, MedDRA preferred term and system organ class – Safety analysis set		AM
3.1.3	Summary of during/post treatment adverse events by subject and coded terms, preferred terms occurring in >=5% of subjects – Safety analysis set		AM
3.1.4	Summary of during/post treatment serious adverse events by subject and coded terms – Safety analysis set	Includes adverse events for which the answer for CRF question "Serious?" in the CRF is "Yes"	AM

No	Title of table/figure	Notes	Shell 

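### SAP 8.4 counts surgical procedures only after discharge, so no planned table identifies an in-hospital re-operation as such, and the counting window shortens with length of stay

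*SAP*

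**What the plan says.** SAP 8.4 sets out to describe two periods, surgery to discharge and the 30-day visit, but confines its first item to the second: "Re-hospitalizations and surgical procedures since hospital discharge [for 30-day (±14 days) visit only". Table 14.2.3 (SAP 10.2.2) repeats the limit with yes/no indicators: "Indication of re-hospitalizations since hospital discharge (d), indication of surgical procedures since hospital discharge [both for 30-day (±14 days) visit only] (d".

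The final contact is anchored on surgery. SAP 2 states: "Subjects will be followed post-operatively through discharge and at 30 days (±14 days) post-surgery".

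Protocol 7.1.4 lists what is recorded before discharge. On the stay itself it asks for "Details of hospital stay including: date of hospital discharge; overall stay in days (admission to discharge); ventilator time (if applicable". The same list also requires adverse events and potential bleeding-related complications, but it names no re-operation item. Protocol 7.1.5, for the 30-day contact, names neither surgical procedures nor re-hospitalisations, so the SAP is the only place where these items are defined.

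Protocol 9.2.8 collects AEs from randomisation "throughout the hospital admission, and until completion of the 30-day follow-up visit", and the AE form includes the action taken. SAP 9.1 reports transfusion volumes separately for the operation, the period up to discharge, and the period after it.

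**The concern.** For an intra-operative haemostat, an unplanned return to theatre is one of the few hard clinical outcomes available, and it bears on the trial's safety objective. The only planned row for surgical procedures starts at discharge, so it excludes the inpatient period by definition. A reader of the tables could see that a bleed had occurred, but could not separate one managed without surgery from one that needed it.

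The start of the window also depends on the child's course after surgery. Because the end is fixed relative to surgery, each extra day in hospital takes a day from the period in which a procedure can be counted. If one arm had more complications and longer stays, it would have less time in which to record an event.

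**Working it through.** The plan gives no event rate, expected stay or power figure on this point, so there is no figure to reproduce. The check has three parts.

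**1. Where could an in-hospital re-operation appear?** The planned tables and listings in SAP 10.2.2 and 10.3.1, set against the question:

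| Planned output | What it would carry | Shows that surgery was needed? |
|---|---|---|
| Table 14.2.3, surgical procedures | Nothing before discharge | No |
| Table 14.2.3, other rows | Elevated care, ventilator use, stay, clinically significant changes | Not stated |
| Tables 14.3.1.1 to 14.3.1.6 | The underlying AE by category or coded term; Table 14.3.1.4 if serious | Not stated |
| Table 14.3.3 | Events linked to TBS re-bleeding; subjects without re-bleeding; transfusion volumes | Not stated |
| Tables 14.1.3.7 and 14.1.3.8 | Any rebleeding, added treatment at the TBS, treatment used for each rebleed | Possibly, but the heading is operative data and no text extends it to a later return to theatre |
| Listings (SAP 10.3) | All non-administrative database fields, by subject | Perhaps, but as a listing and not a count |

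Action taken is recorded for each AE, but no planned table summarises it. Bleeding away from the TBS has no dedicated row.

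**2. Counting window after discharge.**

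Inputs:
- Contact day: 30 − 14 = 16, 30, or 30 + 14 = 44, counted from surgery (SAP 2).
- Stay from procedure to discharge: not given in either document; values below are assumptions.

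Formula: window = max(0, contact day − stay).

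| Assumed stay (days) | Contact day 16 | Contact day 30 | Contact day 44 |
|---|---|---|---|
| 3 | 13 | 27 | 41 |
| 5 | 11 | 25 | 39 |
| 10 | 6 | 20 | 34 |
| 14 | 2 | 16 | 30 |
| 21 | 0 | 9 | 23 |

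For the same contact day, a 5-day stay has 25/20 = 1.25 times the window of a 10-day stay at day 30, and 11/6 = 1.83 times at day 16. The AE collection window does not depend on stay. If procedures were counted from the end of the index operation, the window would be 16, 30 or 44 days by contact day, whatever the stay.

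**3. Weight of one event.** Protocol 8.1 plans 20 subjects per group, so one subject is 1/20 = 5 percentage points of an arm.

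**The case against.** The strongest reply is that the event is not lost. AEs are collected through the whole admission. An event that prolongs hospitalisation is serious (Protocol 9.2.3) and enters Table 14.3.1.4. TBS re-bleeding after 10 minutes must be recorded as an AE (Protocol 7.1.3.4) and is counted in Table 14.3.3. With about 40 children, the listings can be read case by case. This stands. A reader might infer that a return to theatre for bleeding would be in no planned table, and the documents do not support that. What is missing is the re-operation as a separately identifiable count.

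Three other strong readings also fail:
- That a child re-operated before discharge is misclassified. The row is labelled as covering the time since discharge, so a negative entry is correct under its label. The issue is the choice of period.
- That a child still in hospital at the final contact is counted as event-free. No rule covers this case, and the table shells that might settle it are not available, so the point is open.
- That windows range from 41 days down to 2. That comparison pairs opposite ends of the visit range with different stays. At a common day-30 contact, stays of 3 and 14 days give 27 and 16 days.

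It is also fair to say that neither item is a study endpoint, that no test is planned, and that Table 14.2.3 itself reports "length of subject hospital stay from procedure to hospital discharge (days) (c" by arm, so unequal stays would be visible. The Protocol 1 remark that fibrin sealants "reduce the need for repeated procedures by promoting wound healing" is class background tied to wound healing. It does not make re-operation a trial objective. Finally, the eCRF is evidently wider than the protocol's visit lists, since the SAP tabulates items those lists omit. Absence from Protocol 7.1.4 therefore does not prove that re-operation goes uncollected.

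**Conclusion.** The point holds as a gap in reporting. The limit to the post-discharge period is explicit in both SAP 8.4 and Table 14.2.3, and no planned table is stated to identify an in-hospital re-operation as such. The post-discharge window falls day for day with stay and can reach zero; the day-30 loss between assumed stays of 3 and 14 days is 27 − 16 = 11 days.

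The effect on any arm comparison cannot be sized. The documents give neither the length of stay by arm nor the share of re-operations that occur before discharge. One unidentified re-operation is 5 percentage points of a 20-subject arm. The conclusion rests on the SAP text and table list; the eCRF and table shells could show that some of the information is already captured. Priority is low to moderate: no endpoint or effectiveness analysis changes.

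**What to change.** In the first bullet of SAP 8.4 and in Table 14.2.3:
- Count unplanned surgical procedures from the end of the index operation to the final contact.
- Give rows for before discharge, after discharge and total, and one row for re-operation for bleeding. This follows the split that SAP 9.1 already uses for transfusions.
- Keep re-hospitalisation as a post-discharge item, since it can only occur then, with discharged subjects as the denominator.

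Derive the inpatient count from the AE action-taken field and the hospital record. Add a discharge eCRF item only if these do not capture it.

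Cost: a few table rows and, at most, a small eCRF or protocol update. If Protocol 7.1.4 is changed, the amendment must go to the authorities, IRBs and ethics committees under Protocol 15.1. The reported re-operation count may rise, because the inpatient period is then included.

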## 8.5 Statistical/analytical issues

#### 8.5.1 Handling of dropouts or missing data

It is not anticipated that there will be any data missing for treated subjects for the primary endpoint, but if there is, missing data will not be imputed for the primary effectiveness analysis.

Analyses of binary secondary endpoints will consider missing data as failures; missing data for other secondary endpoints will not be imputed.

If there are incomplete dates and calculations (e.g. time since procedure) are needed, the following rules are used (no rules will be applied for missing years; this data would normally be expected to be queried):

- Missing date which includes the procedure data: the rules below are followed unless the derived date is pre-procedure, when the derived date will be 1 day after the procedure.
- Missing day: 15th used

Page 7 of 18

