8.6 Handling of Missing Data

It is not anticipated that there will be any data missing for treated subjects for the primary endpoint, but if there is, missing data will not be imputed for the primary analysis.

Analyses of secondary endpoints will consider missing data as failures.

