#### 5. ANALYSIS SETS

The following three analysis sets defined:

- The Full analysis Set (FAS) consists of all randomized subjects (equivalent to the Intent-to-Treat [ITT] set);
- The Per-Protocol (PP) analysis set (Evaluable set) consists of all FAS subjects who have no major protocol deviations;
- The Safety analysis set consists of all subjects who received treatment.

Major protocol deviations are deviations that have an impact on the primary endpoint, or that have an impact on the randomization assignment. These will be determined prior to database lock.

The primary effectiveness endpoint will be analyzed using the FAS and the PP set. However, the primary analysis will be based on the FAS. The PP analysis will be considered confirmatory.

All secondary effectiveness endpoints (listed in section 8.3) will be analyzed using the FAS set, while safety endpoints (listed in section 9) will be analyzed using the Safety set.

Page 4 of 18 Version: AMENDMENT 1 Date: July 1, 2019

If any patients are mis-randomized (randomized to one treatment, but received the other), then data for the FAS will be summarized 'as randomized', and data for the safety set will be summarized 'as treated'.

If more than 2 patients are mis-randomized, then additional analyses for the FAS will be performed, with patients allocated to treatment groups 'as treated'. Patients who are mis-randomized will be considered major protocol deviations.

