#### 8.2 Primary effectiveness analysis

The primary effectiveness endpoint is the absolute time to hemostasis (elapsed from randomization), defined as the absolute time when there is no detectable bleeding at the Target Bleeding Site (TBS).

The primary effectiveness endpoint will be summarized descriptively by treatment group. The primary endpoint will also be summarized descriptively by treatment group and age group [Neonates (birth to 30 days), Infants and toddlers (31 days to <24 months), Children (2 to 11 years), and Adolescent (12 to <18 years)]. In addition, 95% distribution-free confidence intervals (CIs) for median absolute time to hemostasis will be reported separately for EVICEL and control groups.

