## 10.2.1 In-text tables and figures

These will be produced for the main report in conjunction with the medical writer. These will include, but will not be limited to:

No	Title of table/figure	Notes
F1	Subject disposition	Based on Table 14.1.1.4
T1	Demographic characteristics – FAS analysis set	Summary of Table 14.1.2.1
T2	Surgical procedure – FAS analysis set	Summary of key items from Tables 14.1.3.1-14.1.3.9
Т3	Statistical summary for primary effectiveness endpoint – Per-Protocol and FAS analysis sets (including sensitivity analysis summary)	Summary of Tables 14.2.1.1 and 14.2.1.2
T4	Summary of AEs occurring in >5% of subjects— Safety analysis set	Summary of 14.3.1.3

T=Table F=Figure

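### The primary median has no rule for a randomised subject in whom haemostasis is never observed; such a subject drops out and the reported time is biased short

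*SAP*

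**What the plan says.** - **Endpoint.** SAP 3 and 8.2 define the primary endpoint as the time from randomisation to no detectable bleeding at the target bleeding site (TBS). Neither document gives a value for a subject in whom this is never seen.
- **Estimator.** SAP 8.2 plans a descriptive summary and a distribution-free 95% CI for each arm's median. SAP 10.2.2 lists the endpoint as continuous data. No censoring, Kaplan-Meier or worst-rank rule appears.
- **Population.** The primary analysis uses the full analysis set: "The Full analysis Set (FAS) consists of all randomized subjects" (SAP 5).
- **Missing primary times.** "It is not anticipated that there will be any data missing for treated subjects for the primary endpoint" (Protocol 8.6); if there are any, "missing data will not be imputed for the primary analysis". SAP 8.5.1 has the same rule: "but if there is, missing data will not be imputed for the primary effectiveness analysis". The assurance covers treated subjects only.
- **Missing binary data.** "Analyses of binary secondary endpoints will consider missing data as failures" (SAP 8.5.1).
- **Late haemostasis.** Protocol 7.1.3.4 requires the time to be recorded when haemostasis comes after 10 minutes.
- **Sensitivity analysis.** In-text table T3 is announced as "including sensitivity analysis summary" (SAP 10.2.1). No analysis of that name is defined.

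**The concern.** With no imputation and no censoring, a subject without a time can only fall out of a plain median. If the time is absent because bleeding was never seen to stop, the absence carries information: that subject belongs at the long end of the distribution. Removing it shortens the median, and more so in whichever arm has more such subjects, while the table is still labelled as covering all randomised subjects. The binary endpoints meanwhile count the same subject as a failure, so the primary and secondary results rest on different denominators.

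The study has no hypothesis test on the primary endpoint, so the two medians and their CIs are the main effectiveness result.

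**Working it through.** **Inputs from the documents.** At least 40 subjects, 20 per group (Protocol 8.1). No sample-size calculation was made (SAP 8.2.1), so there is no planned figure to reproduce. The documents give no expected distribution of times and no expected number without a time. Below, k is the number of subjects in a 20-subject arm in whom haemostasis is never observed, and all times in minutes rest on assumed distributions.

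**Step 1. What the rules do to each kind of subject.**

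| Situation | Primary median | Binary endpoints |
|---|---|---|
| Haemostasis timed within 10 min | included | as observed |
| Haemostasis timed after 10 min | included (Protocol 7.1.3.4) | failure at 4, 7 and 10 min |
| Haemostasis seen at a check, exact time missing | leaves | success at that check |
| Haemostasis never observed, or never assessed | leaves | failure at 4, 7 and 10 min |

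The last row carries the bias. The third row loses information but has no built-in direction.

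**Step 2. Rank shift.** The median of n values sits at rank (n+1)/2. Dropping the k longest of 20 puts it at rank (21−k)/2 of the original 20, half a rank lower per subject. The exact CI runs from rank l to rank n+1−l, where l is the largest integer with P(l ≤ B ≤ n−l) ≥ 0.95 and B ~ Binomial(n, ½).

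The last column is the chance that the interval still covers the arm's true median. For limits at ranks l and u of the original 20, it is P(l ≤ B ≤ u−1) with B ~ Binomial(20, ½). It does not depend on the distribution of times.

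| k | n used | Median rank | CI ranks | Nominal coverage | Actual coverage |
|---|---|---|---|---|---|
| 0 | 20 | 10.5 | 6–15 | 95.9% | 95.9% |
| 1 | 19 | 10 | 5–15 | 98.1% | 97.3% |
| 2 | 18 | 9.5 | 5–14 | 96.9% | 93.6% |
| 3 | 17 | 9 | 5–13 | 95.1% | 86.3% |
| 4 | 16 | 8.5 | 4–13 | 97.9% | 86.7% |

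**Step 3. Size in minutes (assumed).** Log-normal times, median 3 min, log-SD 0.6, 20 per arm, by simulation:

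| k longest dropped | Expected median | Change | Expected upper limit |
|---|---|---|---|
| 0 | 3.05 | – | 4.34 |
| 1 | 2.93 | −4% | 4.34 |
| 2 | 2.83 | −7% | 3.98 |
| 3 | 2.72 | −11% | 3.68 |

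Other assumptions give the same direction. With a true median of 4 min, k = 2 gives −8% (log-normal, log-SD 0.7) or −13% (exponential).

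**Step 4. A separate group that never stops bleeding.** Under the Step 3 distribution only 2.2% of times exceed 10 min (1 − Φ(ln(10/3)/0.6)), so the times dropped there are mostly ones that would have been observed. As a check, let k subjects never stop and draw the other 20−k from the same log-normal. The available-times median against the median with those k ranked last is 3.04 against 3.17 (k = 1, −4%), 3.05 against 3.31 (k = 2, −8%) and 3.05 against 3.48 (k = 3, −12%). The size is similar.

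**Step 5. Missing at random.** With 4 of 20 times missing at random (exponential, median 4 min), the expected median is 4.18 against 4.14 with all 20: no material shift.

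**Step 6. Worst rank.** With the k subjects kept as longest, n stays 20, the median stays between ranks 10 and 11, and the CI stays at ranks 6–15. The median is finite while the 11th time is observed (k ≤ 9), and the upper limit while the 15th is (k ≤ 5).

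**The case against.** **Late and failed subjects keep a time.** A reader might infer that the worst outcomes in general vanish from the primary result, or that the median is computed only in subjects who succeeded. The documents do not support that. Protocol 7.1.3.4 requires times after 10 minutes to be recorded, so slow subjects and 10-minute failures with a timed haemostasis stay in. This objection stands and limits the point to subjects in whom haemostasis is never observed. It does not remove the point, because the rule applies only if haemostasis is achieved.

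**A missing time is not always a binary failure.** Protocol 7.1.3.4 lists the 4-, 7- and 10-minute checks separately from the exact time. A subject seen to be haemostatic at a check but lacking an exact time is a success there. This stands, and it rules out giving every missing time the worst rank. With 3 of 20 times missing at random under the Step 3 distribution, blanket worst-ranking would move the expected median from 3.05 to about 3.5 min, an error as large as the one being repaired.

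**Few such subjects are likely.** Severe bleeding is excluded, both products are ready before randomisation, treatment follows immediately, and no missing data are expected in treated subjects. This stands as a limit on size. But randomisation happens when the envelope is opened, before application, and the full analysis set includes subjects never treated. An expectation is also not a rule.

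**The loss would be visible.** SAP 10.2 shows the number of missing observations. That discloses the gap but corrects neither the median nor its CI.

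**The sensitivity analysis may be the per-protocol analysis.** T3 draws only on the full-set and per-protocol tables, so this reading is possible. It would still not address subjects without a time.

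**The analysis is descriptive.** True; no test or decision rule on the primary endpoint is affected.

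**Conclusion.** The point holds in a limited form. For a randomised subject in whom haemostasis is never observed, the planned rules take the subject out of the primary median and bias it short by half a rank, while the same subject fails all three binary endpoints. Under the assumed log-normal, 1 to 3 such subjects in an arm of 20 lower the expected median by 4% to 11%. The CI's coverage of the arm's true median is unharmed at one subject, 93.6% at two and about 86% at three.

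The number affected is an assumption: the documents give none, and with none there is no effect. The direction assumes that the times are absent because bleeding was not seen to stop. The change should be made before database lock, but the gap does not invalidate the design.

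**What to change.** In SAP 8.2 and 8.5.1:

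1. Keep every full-analysis-set subject with no observed haemostasis in the median and its order-statistic CI, with a time longer than every observed time (worst rank). No numeric value need be imputed. If the median or upper limit falls among these subjects, report it as not reached.
2. Where haemostasis was recorded as present at 4, 7 or 10 minutes but the exact time is missing, do not use the worst rank. Treat the time as lying at or before the first check showing haemostasis and after the last earlier check showing bleeding (or after randomisation if there is none). If that interval spans the median or a CI limit, give the result at both ends.
3. Report the number handled under each rule, per arm.
4. In SAP 10.2.1, define the available-times median and CI as the sensitivity analysis in T3.

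Protocol 8.6 carries the same no-imputation sentence, so record the change in SAP 4.

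**Cost.** SAP wording and a little programming; no new data. The reported median and upper limit may be slightly longer, and the mean and SD remain limited to observed times and should be labelled so.
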